## 1.2 Randomization and Treatment Assignments

Subject randomization may be conducted using either a paper-based randomization system or an Interactive Web Randomization System (IWRS). Stratification will be by site and history of receipt of 2017 - 18 influenza vaccine. Proportions of subjects in the various strata will not be pre-specified; rather, the goal will be to achieve an approximately equal distribution of subjects with these characteristics across the various treatment groups.

## 1.3 Unblinding

Treatment assignments are known only to the responsible unblinded vaccine administrators at the trial center. Personnel at the clinical study site including, investigators and study staff, immunology laboratory, and study subjects will remain blinded to individual subject treatment assignments until after the database lock for the final analysis unless emergency unblinding is necessary.

All treatment assignments, vaccine storage and accountability, and/or dosing-related matters will be monitored by a designated “unblinded monitor.” Any deviations will be discussed, documented, and resolved by the unblinded monitor and the unblinded site personnel. Reports provided by the unblinded monitor will be reviewed by designated unblinded personnel at either

Novavax or the clinical research organization (CRO), not involved with the main trial team. No reports from the unblinded monitor will be released to the Trial Master File (TMF) until database lock for Day 364 and official declaration of unblinding is given by Novavax.

## **1.4 Scope of the Analysis Plan**

This statistical analysis plan (SAP) provides a detailed outline of the safety and immunogenicity analyses in accordance with Study Protocol qNIV-E-201 Version 3.0, dated 21 August 2018, and will address the analysis presentation of the unblinded data as well as the final review of all data for the completed study.

An unblinded data review will be conducted upon completion of all Day 28 visits, which will include all available immunogenicity data through Day 28 and safety data (inclusive of clinical laboratory safety assessments for hematology and serum chemistry) through Day 28. Day 364 final analysis will be conducted when all available immunogenicity and safety data through Day 364 have been entered, reviewed, and all queries related to the data have been addressed.

# **2 OBJECTIVES AND ENDPOINTS**

## **2.1 Study Objectives**

### **2.1.1 Primary Objectives**

- To describe the safety and tolerability of Quad-NIV at different doses and formulations (ie, 60 µg HA per A and B strain vs 60 µg HA per A strain and 90 µg HA per B strain), without adjuvant or with 1 of 2 different doses of Matrix-M1 adjuvant (mixed in-clinic or co-formulated in advance of the trial), and of 2 US-licensed comparators, Fluzone HD (Sanofi Pasteur) and Flublok Quadrivalent (Sanofi Pasteur, previously Protein Sciences Corp), in healthy adults  $\geq 65$  years of age. The safety profile will include solicited short-term reactogenicity; 28-day all adverse event (AE) profile; 1-year post-injection medically-attended adverse event (MAE), serious adverse event (SAE), and significant new medical condition (SNMC) profile; and selected pre- and post-vaccination clinical laboratory parameters.
- To demonstrate a Matrix-M1 adjuvant effect by contrasting the immunogenic superiority of Quad-NIV (60 µg HA per A and B strain) co-formulated with 50 µg Matrix-M1 as compared to Quad-NIV (60 µg HA per A and B strain) without adjuvant. Immunogenic superiority will be demonstrated by excluding values  $\leq 1.0$  at the lower 95% confidence bound for the baseline-adjusted ratio of Day 28 post-vaccination HAI titers (ie, GMT adjuvant / GMT no adjuvant) for not less than 2 of 6 influenza strains (ie, any 2 of 4 vaccine-homologous strains and/or 2 antigenically-drifted influenza strains), while no other strain(s) demonstrate a baseline-adjusted ratio of Day 28 post-immunization HAI titers which is significantly  $< 1.0$ .

### **2.1.2 Secondary Objectives**

- To compare the immunogenicity of Quad-NIV (60 µg HA per each A and B strain) with 50 µg of Matrix-M1 co-formulated prior to administration relative to a similar formulation mixed in-clinic and also to 2 US-licensed active comparators, Fluzone HD and Flublok Quadrivalent, in healthy adults  $\geq 65$  years of age, in terms of HAI antibody responses against vaccine-homologous A and B strain(s), and antigenically-drifted influenza strains (multiple informative strains may be tested) at Days 0 and 28 post-vaccination.
- To describe the immunogenicity of formulations of Quad-NIV with increased B-antigen dose (60 µg HA per A strain and 90 µg HA per B strain; and 50 µg of Matrix-M1) or increased Matrix-M1 dose (60 µg HA per A strain and B strain; and 75 µg of Matrix-M1) relative to the “standard” co-formulated Quad-NIV formulation (60 µg HA per each A and B strain; and 50 µg of Matrix-M1) and also to 2 US-licensed active comparators, Fluzone HD and Flublok Quadrivalent, in healthy adults  $\geq 65$  years of age, in terms of HAI antibody responses against all vaccine-homologous A and B strain(s), and antigenically-drifted influenza strains (multiple informative strains may be tested) at Days 0 and 28 post-vaccination.
- To evaluate the longevity of immune responses to Quad-NIV at different doses (ie, 60 µg HA per A and B strain vs 60 µg HA per A strain and 90 µg HA per B strain), with 1 of 2 different doses of Matrix-M1 adjuvant (mixed in-clinic or co-formulated in advance of the trial), and of 2 US-licensed comparators, Fluzone HD and Flublok Quadrivalent, in healthy adults  $\geq 65$  years of age, based on HAI responses against vaccine-homologous and antigenically-drifted influenza strains (multiple informative strains may be tested) post-vaccination on Days 0, 28, 56, 182, and 364.

### **2.1.3 Exploratory Objectives**

- To describe the immunogenicity of Quad-NIV at different doses (ie, 60 µg HA per A and B strain vs 60 µg HA per A strain and 90 µg HA per B strain) and formulations, without adjuvant or with 1 of 2 different doses of Matrix-M1 adjuvant (mixed in-clinic or co-formulated in advance of the trial), and of 2 US-licensed comparators, Fluzone HD and Flublok Quadrivalent, in healthy adults  $\geq 65$  years of age, based on microneutralization (MN) responses to vaccine-homologous and antigenically-drifted influenza strains (multiple informative strains may be tested), at Days 0 and 28 post-vaccination. Note: Due to the time-consuming nature of MN testing, this exploratory objective may be completed in a random subset of participants in each study treatment group after the initial study HAI data are complete and reported in an addendum. Laboratory staff will remain blinded as to treatment assignments until all projected MN tests are complete. Additional time points may also be tested (ie, Days 56, 182, and 364).
- To describe the quality and amplitude of cell-mediated immune (CMI) responses in healthy adults  $\geq 65$  years of age to vaccination with Quad-NIV at different doses (ie, 60 µg HA per A and B strain vs 60 µg HA per A strain and 90 µg HA per B strain) and formulations, without adjuvant or with 1 of 2 different doses of Matrix-M1 adjuvant (mixed in-clinic or

co-formulated in advance of the trial), based on functional T cell responses based on intracellular cytokine analysis. Due to the laborious nature of the cellular assays, they will be performed on subjects from a limited number of preselected sites and results may be reported as an addendum to the main clinical study report.

- To describe the vaccine response among subjects with low baseline HAI titers in terms of fold increases in HAI titers. “Low baseline” will be defined as lowest quintile.

## 2.2 Study Endpoints

### 2.2.1 Primary Endpoints

- Safety and tolerability of Quad-NIV at different doses: Number and percentage (95% CI) of subjects with solicited local and systemic adverse events over the 7 days post-injection (ie, Day 0 through Day 6, inclusive); all adverse events (including adverse changes in clinical laboratory parameters) through 28 days post-injection (ie, Day 0 through Day 27, inclusive); and MAEs, SAEs, and SNMCs – including immunologically-mediated adverse events of special interest (AESIs) - through 1 year post-injection.
- HAI antibody titers specific for the HA receptor binding domains of vaccine-homologous A and B strain(s), and at least 2 antigenically-drifted influenza strains, at Days 0 and 28 post-vaccination. Derived/calculated endpoints based on these data will include:
  - Geometric Mean Titer (GMT) – defined as the antilog of the mean of the log-transformed HAI titers on Day 28.
  - Ratio of GMTs between treatment arms at Day 28 post-vaccination (adjusted for intergroup variation in baseline [pre-vaccination] titers).

### 2.2.2 Secondary Endpoints

- HAI antibody titers specific for the HA receptor binding domains of vaccine-homologous A and B strain(s), and antigenically-drifted influenza strains. Derived/calculated endpoints based on these data will include:
  - GMT, as defined above, on Days 0, 28, 56, 182, and 364.
  - Geometric mean ratio (GMR) – defined as the ratio of post vaccination to pre-vaccination (Day 0) HAI GMTs ( $GMR_{Post/Pre}$ ) on Days 28, 56, 182, and 364.
  - Seroconversion rate (SCR) – defined as proportion of subjects with either a baseline reciprocal (Day 0) titer of  $< 10$  and a post-vaccination reciprocal titer  $\geq 40$ , or a baseline reciprocal (Day 0) titer of  $\geq 10$  and a post-vaccination titer  $\geq 4$ -fold higher on Days 28, 56, 182, and 364.
  - Seroprotection rate (SPR) – defined as the proportion of subjects with a reciprocal HAI titer  $\geq 40$  on Days 28, 56, 182, and 364.
  - Ratio of GMTs between treatment arms at Days 28, 56, 182, and 364 post-vaccination (adjusted for intergroup variation in baseline [pre-vaccination] titers).

### **2.2.3 Exploratory Endpoints**

- Microneutralization (MN) responses: Neutralizing antibody titers specific to vaccine-homologous A and B strain(s) and antigenically-drifted influenza strains, at Days 0 and 28 post-vaccination, as measured by a microneutralization assay. Note: additional time points may also be assessed. Derived/calculated endpoints based on these data will include:
  - GMT – defined as the antilog of the mean of the log-transformed neutralizing titer for a given treatment group.
  - GMR – defined as the ratio of post-vaccination and pre-vaccination neutralizing GMTs within the same treatment group (designated as GMRPost/Pre).
  - SCR – defined as proportion of subjects in a given treatment group with either a baseline reciprocal titer of < lower limit of quantitation (LLOQ) and a post-vaccination reciprocal titer 4-fold higher than the LLOQ, or a baseline reciprocal titer of  $\geq$  LLOQ and a post-vaccination reciprocal titer  $\geq$  4-fold higher than the baseline titer.
  - Ratio of GMTs between treatment arms at Day 28 post-vaccination (adjusted for intergroup variation in baseline [pre-vaccination] titers).
- Proportions of Days 0 and 7 peripheral blood T cell isolates that secrete IL-2, IFN- $\gamma$ , and TNF- $\alpha$  cytokines following *in vitro* restimulation with HA in subjects selected for cellular immune response monitoring.
- HAI titers, as described above.

## **3 ANALYSIS POPULATIONS**

### **3.1 Safety Population**

The Safety Population includes all trial subjects that provide consent, are randomized, and receive the test article. The Safety Population will be used for all safety analyses; and will be analyzed as actually treated.

### **3.2 Intent-to-Treat Population**

The Intent-to-Treat (ITT) Population includes all subjects in the Safety Population that provide any HAI serology data. The ITT Population will be the secondary population used for any immunogenicity analyses and will be analyzed according to treatment as randomized. Analysis using the ITT population will not be performed if it differs from the PP population by less than or equal to 5% of the subjects for each of the 7 treatment groups.

### **3.3 Per-Protocol Population**

The Per-Protocol (PP) Population includes all subjects in the Safety Population that received the assigned dose of the test article according to protocol, have HAI serology results for Day 0 and Day 28, and have no major protocol deviations affecting the primary immunogenicity outcomes as determined by Novavax prior to database lock and unblinding. The PP Population will be the primary population used for immunogenicity analyses.

### **3.4 Discussion of Populations to be Used for Various Analyses**

Subject demographic, baseline data, and safety AE summaries will be based on the Safety Population. All subjects enrolled (randomized) will be used for subject disposition. Immunogenicity summaries and associated statistical analyses will be based primarily on the PP Population and secondarily on the ITT Population.

#### **3.4.1 Protocol Deviations**

A protocol deviation (PD) will be defined as a failure to comply with the requirements set forth in the protocol. PDs may be determined programmatically through the course of the trial. Additionally, all PDs will be entered into the CRO Clinical Trial Management System (CTMS) by the Clinical Research Associates (CRAs) and/or Clinical Trial Managers (CTMs). Examples programmatically-determined PDs are provided in [Table 2](#). This file will provide a description of each protocol deviation and will clearly identify whether or not a deviation warrants exclusion from the PP analysis set. All protocol deviations will be presented in a data listing, with a flag to indicate if a deviation was considered major and resulted in the exclusion of the subject from the PP analysis set.

**Table 2: Programmatically-Determined Protocol Deviations**

Missed Visit
Out of Window Visit
Trial Procedure Not Done
Randomization Error

The following rules will be applied to capture programmatically determined PDs.

- Missed Visit information in protocol deviation from the eCRF will be subservient to those programmatically-determined and will not be used for formal CSR. Missed Visit will not be triggered by “Subject Diary Review” procedure. Missed Visit applies to planned in-clinic visits at Days 0, 7, 28, 56, 182 and 364. Telephone contacts will not be counted as missed visits, though the presence or absence of these visits will be apparent in the data listings. If a subject withdraws from the study early, no subsequent protocol deviations will be checked.
- Out of Window visit will be determined by comparing the actual visit day to the intended visit day. If a subject missed a particular visit (s), (s)he will not be considered as “Out of Window” for that visit but will be counted as “Missed Visit”. Out of Window visit applies to all planned trial visits at Days 0, 7, 28, 56, 182 and 364. Telephone contacts will not be reviewed for visit windows, however the date of occurrence will be present in the data listings.
- Trial Procedure Not Done will include trial procedures (“Physical Exam”, “Vital Signs”, “Clinical Safety Laboratory”, “Serology”, “Trial Treatment Injection” and “Rescue Injection with a licensed seasonal influenza vaccine”) listed in [Appendix 1](#) “Trial

Procedures Schedule” in the protocol. If a subject had “Missed Visit” or “Out of Window Visit”, (s)he will not be counted as “Procedure Not Done” again for the intended visit.

- Randomization Error will be determined by programmer to compare the stratification factors in the EDC to those in the randomization file generated by IWRS vendor. If a subject has discrepancy between the two data sources, (s)he will be flagged as randomization error.

#### **3.4.1.1 Major Protocol Deviations Assessment**

Prior to unblinding, the medical and operational leads will jointly assess protocol deviations and create a consensus final protocol deviations assessment file. Protocol deviations deemed to indicate clear violations of GCP and/or subject consent; or to have a likely effect on the primary immunogenicity outcomes will exclude those subjects from the PP analysis set. In general, the following will be deemed “major”:

- Failure to obtain completely executed and documented informed consent.
- Failure to receive, or document receipt of, the study treatment as randomized.
- For inclusion in the PP Population, failure to provide a sample for serologic analysis on Day 0 and on Day 28.
- Receipt of immunosuppressive medication from Day 0 until the Day 28 visit.
- Documented receipt of any non-protocol influenza vaccine between 6 months prior to Day 0 and the Day 28 visit.
- Other deviations deemed likely by the Sponsor to degrade the immune response to the test article.

## **4 SUBJECT DISPOSITION**

The number of subjects consented, randomized, and vaccinated will be presented by treatment group for all subjects.

The number (percentage) of subjects in the Safety Population, ITT Population, PP Population who have completed the study through Day 28 and through Day 364 will be summarized by treatment group.

The number (percentage) of subjects who discontinue the study prior to Day 364 and the reason for discontinuation (eg, adverse event, investigator decision, lost to follow-up, non-compliance, etc.) will be presented by treatment group. A listing of all subjects in the Safety Population who are discontinued will be presented by treatment group, reason for discontinuation, and day of last study contact. Day of last study contact will be calculated as follows: date of study discontinuation (as recorded on EOS eCRF) minus date of Day 0 vaccination.

The number (percentage) of subjects in the Safety Population with Major Protocol Deviation will be summarized by treatment group. A listing of all subjects in the Safety Population with one or more protocol deviations recorded through Day 28 and through Day 364, will be

provided and will include: treatment group, study day associated with the deviation, protocol deviation category and a description of the deviation as recorded by the site.

## 5 DEMOGRAPHICS AND OTHER BASELINE CHARACTERISTICS

Demographic parameters and other baseline characteristics (age at Day 0 vaccination, gender, ethnicity, race, height [cm], weight [kg], as well as history of receipt of 2017 - 18 influenza vaccine) will be summarized by each treatment group for all subjects in the Safety Population and ITT Population.

Descriptive statistics (total number of subjects [n], mean and standard deviation, median, minimum and maximum values) will be summarized for weight (kg) and height (cm) measurements recorded at Study Day 0. Age (years) at the Day 0 vaccination will be calculated as the closest lower integer result of (Date of Study Day 0 – Date of Birth) / 365.25, and will be summarized using above descriptive statistics.

The number and percentage of subjects for Gender (eg, “Male”, “Female”), Ethnicity (ie, Hispanic or Latino, not Hispanic or Latino), Race (ie, American Indian or Alaska Native, Asian, Black or African American, Native Hawaiian or Other Pacific Islander, and White) will be summarized.

Medical history and physical examination diagnoses/abnormalities will be coded using MedDRA version 20.0. Baseline medical history and physical examination findings recorded on Day 0 (prior to vaccination) will be summarized separately, by MedDRA system organ class (SOC) preferred term (PT), treatment group for all subjects in the Safety Population. Within each SOC and PT, the number and percentage of subjects with at least one abnormality will be presented, respectively. Multiple abnormalities within a given SOC and PT for a subject will be counted once.

## 6 EXTENT OF EXPOSURE

### 6.1 Study Vaccine

Subject vaccination exposure will be summarized as the number and percentage of subjects who received test article at Day 0 by treatment group.

### 6.2 Concomitant Medication

The assessment of concomitant medication use by the subject during the study will coincide with the collection period of adverse events. Concomitant medications recorded on the Concomitant Medications CRF will be summarized by WHO-DRUG Anatomical Therapeutic Chemical (ATC) Term and standardized (generic) medication name version September 2019. The number (percentage) of subjects who record one or more concomitant medications will be presented by treatment group for all subjects in the Safety Population. Multiple occurrences of medication usage for a subject will be counted only once within an ATC term and standardized medication name. The presentation of concomitant medications will include all medications recorded on the Concomitant Medications CRF, including medications with a missing or partial

start date or a start date prior to Study Day 0 vaccination. A separate listing of treatment-emergent new concomitant medications will be presented.

## 7 ANALYSES ADDRESSING PROTOCOL OBJECTIVES

### 7.1 Analyses of Primary Objectives of Immunogenicity

The primary immunogenicity analysis will be based on the PP population. A separate ITT population analysis will not be produced unless > 5% of at least 1 treatment group is excluded from the PP population. No missing data will be imputed.

HAI antibody titers specific for the HA receptor binding domains of vaccine-homologous A and B strain(s), and at least 2 antigenically-drifted influenza strains, at Days 0 and 28 post-vaccination. Derived/calculated endpoints based on these data will include:

- Geometric Mean Titer (GMT) – defined as the antilog of the mean of the log-transformed HAI titers. GMTs will be summarized by treatment group and visit day along with the corresponding 2-sided 95% CIs, by exponentiating the corresponding log-transformed means and their 95% CIs.
- Ratio of GMTs between treatment arms at Day 28 post-vaccination (adjusted for intergroup variation in baseline [pre-vaccination] titers) and two-sided 95% CI will be calculated on log-transformed titers using the analysis of covariance (ANCOVA) with treatment group and baseline (Day 0) measurement as the covariates under two-sided type I error rate of 0.05. No type I error rate will be adjusted. The primary comparison to evaluate the Matrix-M1 adjuvant effect by demonstrating the immunogenic superiority of Quad-NIV is:
  - Group B - qNIV CF A60/B60/M50 (New) vs. Group E - qNIV Unadj A60/B60/M- (Ref)

Note: CF = co-formulated; A = A strain; B = B strain; M = Matrix-M1 Adjuvant.

Note: Two antigenically-drifted influenza strains maybe A/Wisconsin/19/2017 and A/Switzerland/9715293/2013

➤ A sample SAS code for between-group geometric mean ratio (GMRnew/ref) is given below:

```
proc mixed data= fludata;
  by Visit;
  class Treatment;
  model log(HAI_28) = log(HAI_D0) Treatment/noint;
  lsmeans Treatment/cl diff e alpha=0.05;
run;
```

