## 1.1 Study Design

This is a Phase 2, randomized, observer-blinded, active-controlled, dose-finding, formulation-optimizing trial in healthy adults  $\geq 65$  years of age to be conducted in the United States. Up to 1375 eligible subjects will be enrolled and randomized into 1 of 7 treatment groups, as shown in [Table 1](#) below. The base case groups for the demonstration of adjuvant effect, ie, Groups B and E, will each consist of approximately 310 subjects. The remaining groups will consist of approximately 135 (Group D) or 155 (Groups A, C, F, and G) subjects each. Each group will be stratified by site and history of receipt of 2017 - 18 influenza vaccine.

On Day 0, all subjects will receive a study treatment as indicated in [Table 1](#) by intramuscular (IM) injection. Total injection volumes for each treatment group will be 0.5 mL. On Day 28, subjects in Group E will be administered a rescue injection with a 2018 - 19 licensed seasonal influenza vaccine. All other subjects will receive an injection of placebo at Day 28 to maintain trial blind. Trial follow-up for each subject will span approximately 1 year from the Day 0 injection. It is anticipated that a percentage of the randomized trial subjects will not complete the trial. Subjects who withdraw or are discontinued will not be replaced. In addition, all subjects will be offered a 2019 - 20 licensed seasonal influenza vaccine at the last study visit (Day 364).

Enrollment will be divided into 3 stages. Stage 1 will enroll a total of approximately 120 subjects (approximately 20 subjects per treatment group, excluding Group D for which no subjects will be enrolled in Stage 1). Stage 2 will enroll a total of approximately 220 subjects (approximately 20 [Groups A, C, D, F, and G] or 60 subjects [Groups B and E] per treatment group, as per [Table 1](#)). The remainder of the subjects (approximately 1035 subjects total, ie, 115 [Groups A, C, D, F, and G] or 230 [Groups B and E] subjects per treatment group, as per [Table 1](#)) will be enrolled in Stage 3. Progression from Stage 1 to Stage 2 and from Stage 2 to Stage 3 will require favorable review of safety data from the prior stage, against vaccination holding rules.

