- Ratio of GMTs between treatment arms at Days 28, 56, 182, and 364 post-vaccination (adjusted for intergroup variation in baseline [pre-vaccination] titers). P-values may be generated for information and planning of future studies, but will not be adjusted for multiple comparisons. The following treatment group differences will be estimated to address secondary objectives.

- Ratio of GMTs between treatment arms at Days 0 and 28 post-vaccination using ANCOVA to compare the immunogenicity of Quad-NIV (60  $\mu$ g HA per each A and B strain) with 50  $\mu$ g of Matrix-M1 co-formulated prior to administration relative to a

similar formulation mixed in-clinic and also to 2 US-licensed active comparators include:

- Group B - qNIV CF A60/B60/M50 vs. Group A - qNIV Ref A60/B60/M50
- Group B - qNIV CF A60/B60/M50 vs. Group F - FHD3
- Group B - qNIV CF A60/B60/M50 vs. Group G - FBK4
- Ratio of GMTs between treatment arms at Days 0 and 28 post-vaccination using ANCOVA to compare the immunogenicity of Quad-NIV with increased B-antigen dose or increased Matrix-M1 dose relative to the “standard” co-formulated Quad-NIV formulation and also to 2 US-licensed active comparators include:
  - Group C - qNIV CF A60/B60/M75 vs. Group B - qNIV CF A60/B60/M50
  - Group C - qNIV CF A60/B60/M75 vs. Group F - FHD3
  - Group C - qNIV CF A60/B60/M75 vs. Group G - FBK4
  - Group D - qNIV CF A60/B90/M50 vs. Group B - qNIV CF A60/B60/M50
  - Group D - qNIV CF A60/B90/M50 vs. Group F - FHD3
  - Group D - qNIV CF A60/B90/M50 vs. Group G - FBK4
- Ratio of GMTs between treatment arms on Days 0, 28, 56, 182, and 364 using ANCOVA to evaluate the longevity of immune responses to Quad-NIV at different doses and formulations, with 1 of 2 different doses of Matrix-M1 adjuvant, and of 2 US-licensed comparators includes above comparisons and below comparison for each strain.
  - Group C - qNIV CF A60/B60/M75 vs. Group D - qNIV CF A60/B90/M50

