## 9 SAMPLE SIZE CONSIDERATIONS

For safety endpoints, the probability of observing at least 1 adverse event among 135, 155, or 310 subjects for each Quad-NIV formulation is > 90% if the true rate of such events is 1.7%, 1.5%, or 0.8%, respectively. With 135, 155, or 310 subjects for each treatment group, observing no adverse events of interest (eg, vaccine-related SAE) would represent an upper bound of the 1-sided 95% CI on the percentage of such event is 2.2%, 1.9%, or 1.0%, respectively.

This study has a single comparison of 2 treatment groups (Group B vs E) for the primary immunogenicity objective. No formal adjustment for multiple comparisons is planned for the 6 comparisons associated with the 6 strain-specific GMTs. The demonstration of the superiority of Quad-NIV (60 µg HA per A and B strain) co-formulated with 50 µg Matrix-M1 (Group B) as compared to Quad-NIV (60 µg HA per A and B strain) without adjuvant (Group E) requires simultaneous successes of all 6 tests (at least 2 strains meeting the strain-specific superiority criterion and the non-inferiority criterion for the remaining 4 strains). The non-inferiority for this trial will be carried out without a pre-specified margin. Non-inferiority is defined as the 2-sided 95% CI for the ratio of GMTs (Group B / Group E) containing 1.0 (ie, unadjusted 1-sided p-value  $\geq 0.025$  against the null hypothesis of H0: Ratio of GMT  $\leq 1.0$ ). The superiority is defined as the lower limit of the 2-sided 95% CI for the ratio of GMTs (Group B / Group E)  $> 1.0$  (ie, unadjusted 1-sided p-value  $< 0.025$  against the null hypothesis of H0: Ratio of GMT  $\leq 1.0$ ). For other immunogenicity analyses, the purpose is to determine a dose and formulation for the next study based on all available safety and immunogenicity results, including the primary objective analysis. Hence, any statistical analyses (ie, calculations of CIs and p-values) will also be performed without a multiplicity adjustment.

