## **11 COMPUTER METHODS**

Statistical analyses will be performed using SAS® version 9.4 or higher in a Windows environment.

Sample size calculations based on two-sample t-test were performed using PASS 12, version 12.0.3 released on August 6, 2013.

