## 12.2 Adjustments for Covariates

Comparison of GMTs between treatment groups will be adjusted for pre-vaccination titer.

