## 14 CHANGES TO THE SAP

### 14.1 List of Changes from Version 1.1 to Version 2.0

The following changes post unblinding were made to be consistent with previously published data (Couch 2014) from Version 1.1 to Version 2.0 of the Statistical Analysis Plan.

Reason for Changes:

- Between treatment comparisons for the CMI results were performed at 2-sided 0.1 Type I error rate level and 2-sided 90% CIs for inference (Section 12.).
- For the CMI measurements that require log transformation will be assigned a value of 1 count per million cells for those reported as 0 (section 12).

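### The GMT-ratio ANCOVA leaves out the stratification factors and enrolment stage, which costs a little precision and exposes the Group D comparisons to a stage imbalance

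*SAP*

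**What the plan says.** SAP 1.2 states: "Stratification will be by site and history of receipt of 2017 - 18 influenza vaccine". Protocol 3.3 says the same. SAP 1.1 and Table 1 divide enrolment into three stages with different allocation ratios. Stage 1 takes about 20 per arm, "excluding Group D for which no subjects will be enrolled in Stage 1". Stage 2 takes 20 per arm, but 60 in B and E. Stage 3 takes 115 per arm, but 230 in B and E.

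The analysis model reflects none of this. SAP 7.1 computes the ratios "using the analysis of covariance (ANCOVA) with treatment group and baseline (Day 0) measurement as the covariates", and its sample code contains only log Day 0 titer and treatment. SAP 12.2 sets the same rule for all such comparisons: "Comparison of GMTs between treatment groups will be adjusted for pre-vaccination titer". Protocol 10.4.2 agrees. Neither document adds site, vaccination history or stage, even as a sensitivity analysis; vaccination history is only tabulated at baseline (SAP 5). SAP 7.2 applies the same ANCOVA to D vs B, D vs G, C vs D and "Group D - qNIV CF A60/B90/M50 vs. Group F - FHD3", without limiting the comparison to subjects enrolled in the same stages.

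**The concern.** There are two separate problems.

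**Strata.** Stratified randomisation balances site and vaccination history across arms. A model that ignores them leaves their effect in the residual variance, so the reported interval is wider than the real sampling error. For superiority of B over E this is conservative. The primary criterion has a second part, however. SAP 9 says: "Non-inferiority is defined as the 2-sided 95% CI for the ratio of GMTs (Group B / Group E) containing 1.0". A wider interval contains 1.0 more often, so a check meant to catch a strain on which the adjuvant does worse becomes slightly easier to pass.

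**Stage.** This is a question of bias. Stage 1 subjects in B, C, F and G could not have been randomised to D, so for D they are non-concurrent comparators. Randomisation does not protect D contrasts across stages; only the model can. SAP 9 says the non-primary immunogenicity results, taken with all other results, are to inform the dose and formulation for the next study.

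**Working it through.** **1. The plan's own power figure.** Inputs from SAP 9: 295 evaluable per group, log10 SD 0.4 to 0.6, two-sided 0.05. SAP 11 gives the method: "Sample size calculations based on two-sample t-test were performed using PASS 12". At SD 0.6 and 1.4-fold, the difference is log10(1.4) = 0.1461 and SE = 0.6 × √(2/295) = 0.0494. The t-test gives 84.0%, against 84% in SAP Table 6. SD 0.5 with 1.3-fold gives 78.9%, against 79%. The stated power reproduces and does not depend on the omitted factors.

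**2. Omitted strata, B vs E.** Let R² be the share of the variance left after baseline titer that the strata explain. The documents do not give it; 2% to 10% is assumed. The SDs in SAP 9 are used as residual SDs for illustration; the SAP does not say they are baseline-adjusted. With the strata balanced by design:

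- SE_model = SD × √(2/295); SE_true = SE_model × √(1 − R²)
- excess CI width = 1/√(1 − R²) − 1
- actual two-sided error = 2·P(Z > 1.96/√(1 − R²))
- power, strata omitted = P(Z > (1.96·SE_model − δ)/SE_true)
- power, strata included = P(Z > 1.96 − δ/SE_true)

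| R² | CI too wide by | Actual error (nominal 5%) | Power, SD 0.6, 1.4-fold: omitted / included | Power, SD 0.5, 1.3-fold: omitted / included |
|---|---|---|---|---|
| 2% | 1.0% | 4.8% | 84.3% / 84.8% | 79.3% / 79.8% |
| 10% | 5.4% | 3.9% | 85.4% / 87.7% | 80.3% / 83.1% |

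For the second part of the criterion, take a strain with true ratio 0.85 (assumed), SD 0.5 and R² 10%. Then δ = log10(0.85) = −0.0706, SE_model = 0.0412 and SE_true = 0.0391. The chance of not being significantly below 1.0 is P(Z > (−1.96 × 0.0412 + 0.0706)/0.0391) = 60% with the strata omitted, and P(Z > −1.96 + 0.0706/0.0391) = 56% with them included.

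**3. Stage mix, from SAP Table 1.**

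| Arms | Stage 1 | Stage 2 | Stage 3 | Stages 1-2 |
|---|---|---|---|---|
| A, C, F, G (155) | 12.9% | 12.9% | 74.2% | 40/155 = 25.8% |
| B, E (310) | 6.5% | 19.4% | 74.2% | 80/310 = 25.8% |
| D (135) | 0% | 14.8% | 85.2% | 20/135 = 14.8% |

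The ratio is multiplied by 10^(difference in share × stage effect in log10). The stage effect net of baseline is not in the documents; 0.1 to 0.2 log10 is assumed.

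- *Stages 1-2 differ from Stage 3.* The share difference is 25.8% − 14.8% = 11.0 points for D against any other arm. 10^0.011 to 10^0.022 is a shift of 2.5% to 5% in D vs B, F and G and in C vs D. Other contrasts shift by 0. For D vs F at SD 0.5 with 128 and 147 evaluable, SE = 0.5 × √(1/128 + 1/147) = 0.060, so the shift is 0.2 to 0.4 SE.
- *Only Stage 1 differs.* The share difference is 12.9 points for D vs F, D vs G and C vs D, a shift of 3% to 6%. It is 6.5 points for D vs B, B vs A, B vs F, B vs G and C vs B, a shift of 1.5% to 3%.
- B vs E, C vs F and C vs G have identical stage splits: 0 in both cases.

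For the error rate of D vs F, take a 1.5-fold Stage 1 effect. The bias is 0.129 × log10(1.5) = 0.0227, which is 0.31 SE at SD 0.6 (SE 0.0725) and 0.47 SE at SD 0.4 (SE 0.0483). The nominal 5% test then runs at 6.1% and 7.6%. With a 1.2-fold effect it runs at 5.2% to 5.5%.

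**4. Simulation check.** Table 1 counts, 2,000 runs, no true arm difference. With Stages 1-2 raised by 0.2 log10, the mean D/F ratio was 0.948 from the baseline-only model and 0.997 with a stage term. With only Stage 1 raised it was 0.942 and 0.999. B/E stayed at 0.999 to 1.000 in both models.

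**The case against.** The strongest reply is that no harm to the primary analysis is shown. B and E have the same stage counts (20/60/230), superiority is conservative, and the power is intact. The 60% vs 56% result needs the top of the assumed R² range and an assumed ratio of 0.85, and owes much to a non-inferiority rule without a margin, which is a separate matter. All of that is right, and it is why the point is modest.

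The sizes also rest on assumptions. The documents give no R², number of sites, blocking scheme or stage effect. SAP 1.2 aims only for approximately equal distribution across arms, so the width and error figures are upper bounds for a given R². A stage effect of 0.1 to 0.2 log10 is 1.26- to 1.58-fold, about the size of the adjuvant effect the trial is powered for. The stages are safety gates, and no change of eligibility, product or assay between them is described. This stands as a caution on size: the documents neither report nor exclude a stage effect.

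The D contrasts are descriptive, with p-values for information only. That lowers the stakes but does not justify an avoidable bias in estimates meant to guide formulation choice.

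Finally, SAP 2.0 already records changes made after unblinding, so replacing the specified model now would be wrong. That is correct, and the fix allows for it.

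**Conclusion.** The point holds as an improvement the plan should make; it does not show a failed primary analysis. The model does not reflect the randomisation. For B vs E the cost is intervals about 1% to 5% too wide, given an assumed R² of 2% to 10%, with a slight loosening of the condition that no strain is significantly worse. Stage causes no bias there. For Group D the ratios rest partly on non-concurrent comparators. They would move by 1.5% to 6%, depending on the contrast and on which stage differs, if a stage effect of 0.1 to 0.2 log10 remained after baseline adjustment. That is well under one standard error. The stage shares and the content of the model are facts of the documents; R² and the stage effect are assumptions.

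**What to change.** In SAP 7.1, 7.2, 12.2 and the sample code, use one model for all GMT ratios:

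`class Treatment VaxHist Site Stage;`
`model log(HAI_28) = log(HAI_D0) Treatment VaxHist Site Stage;`

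Fit site as a fixed effect, with small sites pooled by a size rule written down before unblinding. Keep the baseline-only model as a sensitivity analysis. Restricting the Group D comparators to Stages 2-3 is an optional check, not needed once stage is in the model.

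Where the data are already unblinded, do not replace the model. SAP 14.1 records: "The following changes post unblinding were made to be consistent with previously published data". In that case the baseline-only ANCOVA stays as the pre-specified analysis, and the adjusted model is reported as a labelled supplementary analysis, chiefly for the Group D ratios.

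The cost is SAP wording and three class terms. The stratification factors are already held in the EDC and the randomisation file (SAP 3.4.1), and stage is known from enrolment. The model loses a few degrees of freedom; the site share of these cannot be stated because the number of sites is not given. With the Table 1 counts, a stage term raises the SE of D vs F from 0.1177 × SD, which is √(1/135 + 1/155), to 0.1184 × SD. That is about 0.6% whatever the SD. The SE of B vs E does not change.
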